1. BACKGROUND

1.1 Summary and Study Design

The goal of the study is to provide a high-intensity exercise program for older Veterans that can be widely disseminated and attenuates processes underlying aging. The study is a randomized trial of 12-weeks of high-intensity functional circuit exercise that will be broadcasted from the Salem VAMC to older Veterans living with HIV in the Atlanta and Baltimore VAMCs. Our primary objective is to determine the effect of VTEL exercise compared to sedentary controls on cardiorespiratory fitness, anaerobic threshold, and O₂pulse based on gas exchange at peak exercise (Aim 1) in addition to sarcopenia and frailty (Aim 2). We also will investigate the effect of VTEL exercise on DNA methylation as a biomarker of advanced aging and determine correlates with biomarkers of systemic inflammation (Aim 3). The sedentary control group will be offered the 12-week exercise training and follow-up testing in a delayed entry design to ensure equity of the benefits of exercise to all participants.

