Phenotypic Outcomes (AIM 1) and Biomarker DNA Age (AIM 2): We hypothesize that the VTEL high-intensity circuit exercise intervention will increase cardiorespiratory fitness and decrease sarcopenia and frailty (AIM 1) and decrease DNA Age (AIM 2). ANOVA models will be used with dependent variables of cardiorespiratory fitness (VO₂peak, 2-minute step test) and DNA Age (years). Logistic or multinomial models will be used with dependent variables of sarcopenia (present/not present) and frailty (robust/pre-frail/frail). Secondary analyses will be performed that use the individual components of composite outcome as their own dependent variable (e.g., lean mass and strength from sarcopenia). ANCOVA will be used to test for between group difference by time (pre/post exercise). Baseline performance and demographic and clinical characteristics will be included in models to assess and adjust for known potential confounding factors based on our experience with older HIV+ adults. We do not expect significant variability or effect from HIV-related factors (e.g., antiretroviral therapy, viral load) since we will use our previous established eligibility criteria. We do not anticipate needing to adjust for sex or race since each individual will function as their own control. Nutritional analyses of macro and micronutrients will be performed to measure any change during the study, and if present, will be tested for within group and between group effects. A similar approach will be applied to smoking exposure, which will be quantitated at baseline and follow-up testing. Treatment fidelity will be measured as percent of AEX time at target heart and entered in ANOVA models. For future planning, feasibility analyses will include calculation of rates for enrollment, retention, and attendance overall and by HIV group. Aggregate data will be collected on adverse events and reasons for lost to follow-up.

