Analyses will include participants who drop out before completion of the 12-week intervention period by way of multiple imputation. This intention to treat approach will investigate factors that may affect compliance and difficulty with exercise training, including soreness and medical comorbidity. If the pattern of missing data is missing completely at random, or simply at random, our multiple imputation should eliminate bias due to loss to follow-up. Because the participants will be recruited from clinic-based VA cohorts, we will be able to obtain clinical data from participants who drop out of the study, but remain in clinical care, to determine if drop-out was related to medical conditions that may influence outcomes. Thus, we will be able to estimate bias introduced by loss to follow-up. If there is sufficient information, we may be able to model the drop-out process and adjust our analyses for loss to follow-up even if the missing data pattern is non-ignorable. If 36 training sessions cannot be completed in 12 weeks, then total training time will be tracked, and incorporated into the data analysis.

DNA Methylation (AIM 3): We will examine the change of methylation levels after 12 weeks for each candidate marker using ANOVA models. To examine epigenetic association with each outcome, we will fit the linear regression model as follows: where Y_i is the quantitative outcome measurement, Z_i is the vector of covariates including age, race, smoking status and leukocyte proportions, and E_i is the candidate epigenetic marker. ANCOVA will be used to test for between group difference by time (pre/post exercise). The candidate epigenetic markers will involve individual CpG sites previously identified and discussed in detail section D4c. We will extend this linear regression model to account for batch/chip effects and

longitudinal measures using a linear mixed model. We will adjust the significance threshold for multiple testing using Bonferroni correction ($p < 0.05 / \text{number of tests}$).

Sample Size Estimates:

AIM 1. Paired t-test was used to test for a mean change given a range of correlation between pre and post values with assumptions of $\alpha = 0.05$ and 80% power. (Mean (SD) values for the VO_2peak are from our current high-intensity AEX + RT trial in HIV+ Veterans (Table 3). Data for 2-minute step test are from our VTEL Gerofit exercise program (C3). Values for chair stands are results from a 10-week RT in older men.⁴⁶ We will have adequate

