
sample size even with attrition as high as 40% and a correlation of within person values as low as 0.3.

AIM 2: Since change in DNAm

AIM	Dependent Variable	Pre/ Post Intervention		Sample Size		
		Pre-Mean (SD)	Post-Mean (SD)	correlation pre/post		
		0.3	0.5	0.7		
1	$\text{VO}_2\text{peak, L/min}$	2.17(0.13)	2.46(0.14)	4	3	2
	2-min. step test	67 (18)	86 (17)	16	14	9
	Chair stands ⁴⁶	17.8 (5.4)	25.4 (5.6)	8	7	5
2	DNAm Age, yrs ²³	62(10.8)	68.7(10)	29	21	14

Age with exercise training is unknown, we used values from our observational study of 19 male Veterans before and after antiretroviral therapy was started.²³ We will have adequate sample size even with attrition of 28% and a correlation of within person values as low as 0.3.

AIM 3: As summarized by Tsai and Bell, epigenetic data generated by EWAS have two additional factors that affect power, stability of CpG sites and their variance within a biological sample.⁴⁷ They performed power simulations based on micro-array based datasets (e.g., Illumina 450K) with the assumption that disease risk is affected by a single CpG site. Using Wilcoxon signed-rank test for paired study design (one sample), 80% power and $\alpha < 0.05$, they generated sample size estimates based on percent methylation difference (p.1437).⁴⁷ Denham reported a 11.6% methylation difference after 4 weeks of AEX in a single CpG site in the EGF gene, which also showed decreased mRNA expression.⁴⁸ On the basis of this literature, a sample size of 34 participants is sufficient to find an 11% difference in methylation of a relevant candidate gene with exercise.

2.3.f Data Sharing and Publication

Final data sets underlying all publications resulting from the proposed research will be shared outside the VA. A Limited Dataset (LDS) will be created and shared pursuant to a Data Use Agreement (DUA) appropriately limiting use of the dataset and prohibiting the recipient from identifying or re-identifying (or taking steps to identify or re-identify) any individual whose data are included in the dataset. Data sharing and preservation will enable validation of results and advancing science by broadening the value of research data for intra and inter disciplinary developments ultimately benefiting the scientific community, industry, and the public at large.

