3 STUDY METHODS

3.1 Study Design

This study is a multi-site exercise intervention for Veterans receiving care at the Atlanta and Baltimore VAMCs that will randomize approximately 80 participants (40 per site) at these VAMCs, herein referred as enrollment sites. The intervention is 12-weeks of high-intensity functional circuit exercise performed 3 times weekly in a supervised group setting. Exercise training will be led by an exercise physiologist at the Salem VAMC (coordinating site) and broadcast to the enrollment sites. HIV-infected Veterans 50 years of age and older will be enrolled at the Atlanta and Baltimore VAMCs. Eligible participants will be randomized to exercise training (N=40) or control (N=40) groups. All participants will undergo baseline testing and follow up testing after 12 weeks at their respective enrollment site. Participants in the Control Group will be instructed to maintain their baseline sedentary lifestyle (as defined in eligibility criteria) during the 12-week intervention period. After follow-up testing is complete, participants in the control group will have the option of completing 12-week exercise training (delayed entry exercise) which will be a combined home and center-based exercise program. Pre-post exercise testing will be conducted in these participants to gauge individual progress and provide individual feedback that is a benefit of study participation, but these results will not be part of the randomized trial analyses.

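### Aims 1 and 2 are sized by a one-group paired t-test, but the trial compares two arms, so the stated adequacy for DNAm Age at 28% attrition and r = 0.3 is not met

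*Combined protocol and SAP*

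**What the plan says.** Section 2.3.e, Sample Size Estimates, says for Aim 1 that a "Paired t-test was used to test for a mean change given a range of correlation between pre and post values", at alpha 0.05 and 80% power. The accompanying table gives a pre mean (SD), a post mean (SD) and one required number for each of r = 0.3, 0.5 and 0.7. For DNAm Age (Aim 2) the entries are 62 (10.8) and 68.7 (10) years, and 29, 21 and 14 participants. The effect is borrowed: "we used values from our observational study of 19 male Veterans before and after antiretroviral therapy was started". The conclusion for Aim 2 is: "We will have adequate sample size even with attrition of 28% and a correlation of within person values as low as 0.3".

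The design and analysis are between arms. Section 1.1 sets the primary objective as to "determine the effect of VTEL exercise compared to sedentary controls". Section 3.1 states: "Eligible participants will be randomized to exercise training (N=40) or control (N=40) groups". The paragraph of 2.3.e that covers Aims 1 and 2, including DNAm Age, states: "ANCOVA will be used to test for between group difference by time (pre/post exercise". Section 3.1 also says of the delayed-entry pre/post data from controls that "these results will not be part of the randomized trial analyses", so those data cannot enlarge the exercise group.

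For Aims 1 and 2 the document gives no between-arm power or sample size, and it states no expected change in controls.

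**The concern.** A paired calculation gives the number of people needed to show that one group changed. A comparison of two randomised arms also carries the sampling variance of the control arm, so the paired n is not the n per arm. For the same mean change and the same SD of change, the between-arm test needs roughly twice the paired number in each of two arms.

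If the adequacy sentence is taken at face value, a null between-arm result for DNAm Age would be read as coming from a study with 80% power, which it would not have. A trial sized on pre/post change also invites a retreat to the within-arm test when the between-arm test fails, and that gives up the benefit of randomisation. The plan's remark that each individual acts as their own control points the same way.

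**Working it through.** **Inputs (2.3.e table and text; 3.1).** Mean difference 68.7 − 62 = 6.7 years; SDs 10.8 (pre) and 10 (post); r = 0.3, 0.5, 0.7; alpha 0.05; power 80%; 40 per arm. Sidedness is not stated, but two-sided reproduces the DNAm Age row and one-sided does not (23/17/11). Zero change in controls is my assumption, because the document gives none. All powers use the noncentral t distribution.

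**Reproducing the plan's figure.** SD of change = √(10.8² + 10² − 2·r·10.8·10) = 12.32, 10.42 and 8.09 for the three correlations. The standardised change at r = 0.3 is 6.7/12.32 = 0.544. A two-sided paired t-test then needs 29, 21 and 14, exactly as printed. The attrition claim follows from one arm: 40 × 0.72 = 28.8, about 29.

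**The between-arm comparison with the same inputs.** Two models are relevant.

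- Change score (equivalently a group-by-time test): the SD is the SD of change, 12.32 at r = 0.3, so d = 0.544.
- ANCOVA on the 12-week value adjusted for baseline: residual SD = SD·√(1 − r²). With the follow-up SD of 10 this is 10·√0.91 = 9.54 and d = 6.7/9.54 = 0.702. With SD 10.8 it is 10.30 and d = 0.650.

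Number per arm for 80% power at r = 0.3: change score 55; ANCOVA 33 (SD 10) or 39 (SD 10.8). Allowing for 28% attrition, 55/0.72 gives 77 and 33/0.72 gives 46 per arm, against 40 randomised.

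| Completers per arm | r | Change score | ANCOVA, SD 10 | ANCOVA, SD 10.8 |
|---|---|---|---|---|
| 29 (28% attrition) | 0.3 | 53% | 75% | 68% |
| 29 | 0.5 | 67% | 83% | 76% |
| 29 | 0.7 | 87% | 94% | 90% |
| 28 (30% attrition) | 0.3 | 51% | 73% | 67% |
| 28 | 0.5 | 66% | 81% | 75% |
| 28 | 0.7 | 86% | 93% | 89% |

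The 28-per-arm rows use the 30% attrition expected in section 3.3.a (40 × 0.70 = 28). There, at r = 0.3, the difference detectable with 80% power is 9.4 years by change score and 7.3 years by ANCOVA with SD 10, against the assumed 6.7.

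**Aim 1.** With 24 per arm (40% attrition, the plan's own worst case), r = 0.3 and the less efficient change-score test, between-arm power at the assumed effects is above 99% for VO₂peak, 87% for the 2-minute step test and 98% for chair stands. The wrong test was used here too, but the conclusion survives.

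**Side observation.** The chair-stand row also reproduces (8/7/5), but two Aim 1 rows do not: the step test is printed as 16/14/9 and computes to 12/9/7, and VO₂peak is printed as 4/3/2 and computes to 5/4/4. This does not affect Aim 2.

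**The case against.** The strongest reply is that the plan names ANCOVA and says baseline performance and other characteristics will be in the models. The change-score figures (55 per arm, 53%) then describe a less efficient analysis than the one intended, and the gap is 33 against 29 per arm, or 75% against 80%. This is a fair limit on size. The ANCOVA figure should lead, and the change-score figure matters only because the wording about a difference by time leaves that reading open. It does not bring power to 80%.

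Further covariates could help. At 29 per arm, 80% is reached if baseline and covariates together explain about 20% of the variance with SD 10, or 31% with SD 10.8; baseline at r = 0.3 explains 9%. The document gives no such figure, so this shows sensitivity rather than adequacy.

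A higher correlation also helps. ANCOVA with SD 10 passes 80% at r = 0.5. The plan's sentence, however, claims adequacy down to 0.3.

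Section 3.3.a and Table 5 plan for 80 completers, whereas 1.3 and 3.1 count 80 randomised. With 40 completers per arm, ANCOVA power at r = 0.3 would be 82% to 87% (change score 67%). That conflict needs settling, but the 28% claim fits only 40 randomised per arm.

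Multiple imputation is offered in the plan against bias. It does not restore the information lost when the only follow-up value is missing.

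Finally, section 1.1 ties the comparison with controls to the primary objective, and Aim 2 in 1.3 does not repeat it. The between-arm test for DNAm Age rests on the 2.3.e paragraph, which covers Aims 1 and 2 together. That is sufficient.

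**Conclusion.** The point holds. The calculation answers a one-group question, and the Aim 2 adequacy statement is wrong for the comparison the trial plans to make. Under the conditions the plan names (29 per arm, r = 0.3, 6.7 years), between-arm power is 75% by ANCOVA with SD 10, 68% with SD 10.8 and 53% by change score. No version reaches 80%.

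The result assumes two-sided 0.05, no change in controls and 40 randomised per arm. It is specific to Aim 2 at the low end of the correlation range; the continuous Aim 1 outcomes in the table are not endangered. The 6.7 years is itself uncertain: it is an increase seen around the start of antiretroviral therapy, the plan hypothesises a decrease, and it says the change with exercise is unknown. All the powers above are therefore conditional on that magnitude.

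**What to change.** - Replace the paired calculation for Aims 1 and 2 with a two-arm calculation for one named model: the 12-week value on arm, baseline value and site.
- Delete the claim of adequacy at 28% attrition and r = 0.3. State instead, for example, that with 28 completers per arm ANCOVA gives 73%, 81% and 93% power for a 6.7-year difference at r = 0.3, 0.5 and 0.7. Say that this uses the follow-up SD of 10 and no change in controls; with SD 10.8 the figures are 67%, 75% and 89%.
- Say whether 80 is the number randomised or the number completing, and make 1.3, 3.1 and Table 5 agree.
- State that within-arm pre/post tests are descriptive only.
- Recompute the Aim 1 rows on the same two-arm basis. Check Aim 3 as well, since its 34 participants also come from a one-sample paired design.

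The cost is rewording of the sample size section. No participants are added; one stated figure becomes less favourable.

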Feasibility of the project is supported by investigators with a track record of collaboration and the existing infrastructure including experience staff, well-defined population, and available exercise, VTEL, and lab equipment. Based on prior exercise trials we have conducted in this population, we expect a 33% eligibility failure rate and a 30% attrition rate. Due to the COVID hold in 2019-2000, first study year, no participant activity occurred and a 1-year cost-extension has been awarded which will allow for completion of 40 participants per site to complete the exercise trial within the project period (Table 5).

Table 5	Y 2				Y 3				Y 4				Y 5				total
	1	2	3	4													
Quarter	1	2	3	4	1	2	3	4	1	2	3	4	1	2	3	4	
Completers	2	6	6	6	6	6	6	6	6	6	6	6	6	4	2		80
AVAMC	1	3	3	3	3	3	3	3	3	3	3	3	3	2	1		40
BVAMC	1	3	3	3	3	3	3	3	3	3	3	3	3	2	1		40

Eligibility

HIV+ adult men and women of all races and ethnicities who are 50 years of age and older will be eligible. Eligibility criteria are based on our exercise research in older HIV+ adults and American College of Sports Medicine guidelines and are designed to minimize attrition, maximize safety, and limit confounding

factors. Of note, smoking is not an exclusion criterion since approximately 70% of the otherwise eligible HIV+ Veterans are smokers, and if excluded would decrease the study's generalizability.

Inclusion Criteria: Participants will be on antiretroviral therapy with HIV viral suppression because HIV viremia affects DNA methylation and DNA age. Only sedentary adults will be eligible (not engaging in structured activity for exercise ($\geq 1/\text{week}$)).

Exclusion Criteria: Specific eligibility criteria are listed in Table 6 below and include objective cut-off limits designed to maximize safety and minimize attrition but not prohibitively limit enrollment and maintain generalizability. Eligibility will be determined by information collected by a clinician study investigator during the eligibility visit which occurs after informed consent is obtained. The eligibility visit includes history and physical exam (H&P), review of the electronic medical record, and resting ECG. The following eligibility checklist was used for IRB submission at the enrollment sites:

Table 6. Eligibility Checklist		
*based on date of H&P		
Inclusion Criteria		
Yes	No	
		Veteran living with HIV and under care at VAMC
		50 years of age and older
		Stable antiretroviral therapy (ART) (same ARV medications within 3 months)

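### Aim 3 is called sufficient at 34 participants with no attrition allowance; if 80 is the number randomised, the expected 30% attrition leaves about 28 exercise pairs, and the documents also use 80 as the number completing

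*Combined protocol and SAP*

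**What the plan says.** **Aim 3 sizing (2.3.e, Sample Size Estimates).** The plan relies on published power simulations: "Using Wilcoxon signed-rank test for paired study design (one sample), 80% power", with alpha 0.05. It concludes that "a sample size of 34 participants is sufficient to find an 11% difference in methylation of a relevant candidate gene with exercise". It prints no standard deviation for the methylation change and no attrition allowance.

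**Aims 1 and 2 (same section).** Both state the attrition they can absorb. Aim 1 claims 40%. For Aim 2 the plan says: "We will have adequate sample size even with attrition of 28% and a correlation of within person values as low as 0.3". The accompanying table requires 29 participants at that correlation.

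**Numbers randomised.** Section 1.3 describes 80 Veterans randomised to exercise or control. Section 3.1 says the study "will randomize approximately 80 participants (40 per site) at these VAMCs" and "Eligible participants will be randomized to exercise training (N=40) or control (N=40) groups". It also keeps the delayed-entry exercise results of the control group out of the randomised trial analyses.

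**Attrition and completion (3.3.a, Enrollment and Completion Targets).** The investigators write "we expect a 33% eligibility failure rate and a 30% attrition rate". The next sentence says the extended project period allows 40 participants per site to complete. The Completers row of Table 5 totals 80, or 40 per site.

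**Missing data (2.3.e).** Participants who drop out are kept in the analysis by multiple imputation.

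**The concern.** The Aim 3 figure comes from a one-sample paired test of change with exercise, so what counts is the number of exercise participants with both samples. Delayed-entry data are excluded, so only the exercise arm supplies them. Setting 40 randomised to exercise beside 30% expected attrition gives fewer pairs than the plan calls sufficient. Aim 3 is also the only aim whose sample size is not set against any attrition rate.

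At stake is how a null methylation result would be read. If the sufficiency statement stands, such a result could be reported as coming from an adequately powered comparison when the plan's randomised number and attrition do not deliver the required pairs. Behind this lies a second problem: the same figure of 80 serves as both the number randomised and the number completing, so the documents do not settle how many pairs are planned.

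**Working it through.** **Inputs**

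| Quantity | Value | Source |
|---|---|---|
| Required for Aim 3 | 34 | 2.3.e |
| Test, power, alpha | signed-rank, paired, one sample; 80%; 0.05, sidedness not stated | 2.3.e |
| Randomised to exercise | 40 of about 80 | 3.1; total also in 1.3 |
| Expected attrition | 30% | 3.3.a |
| Planned completers | 80 | 3.3.a, Table 5 |
| SD of methylation change | not printed | – |

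**Step 1. Can the plan's 34 be reproduced?** No. It comes from an outside simulation paper, and no SD is given. The neighbouring Aim 2 row can be reproduced. At r = 0.3 the SD of change is √(10.8² + 10² − 2 × 0.3 × 10.8 × 10) = 12.32, so the standardised change is (68.7 − 62)/12.32 = 0.544. A two-sided paired t-test at 0.05 with 80% power (noncentral t) then needs 29. The same method gives 21 and 14 at r = 0.5 and 0.7, matching the table.

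**Step 2. Is 40 the arm size before or after losses?** The Aim 2 allowance answers this for the sample-size section: 40 × (1 − 0.28) = 28.8, about the 29 required. That section therefore treats 40 as the arm before attrition.

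**Step 3. Pairs if 80 is the number randomised.**
- Expected pairs: 40 × (1 − 0.30) = 28, which is 34 − 28 = 6 short.
- Largest attrition that still leaves 34: 1 − 34/40 = 15%.
- Number randomised to exercise for 34 pairs at 30% attrition: 34/0.70 = 48.6, so 49.

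**Step 4. Pairs if 80 is the number completing.**
- Table 5 completers: 2 + 12 × 6 + 4 + 2 = 80, so about 40 exercise pairs at 1:1, above 34.
- Number randomised to obtain 80 completers at 30% attrition: 80/0.70 = 114.3, so about 115.

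**Step 5. Illustration of size.** Assume that 34 pairs give exactly 80% power for an 11% difference at two-sided alpha 0.05. For a paired t-test the implied standardised change is 0.495.

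| Exercise pairs | Paired t (0.495) | Signed-rank, simulated (0.51) |
|---|---|---|
| 34 | 80% | 80% |
| 28 | 71% | 71% |
| 40 | 86% | 87% |

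With 28 pairs, 80% power needs a standardised change of 0.549. That corresponds to 11% × 0.549/0.495, or about 12.2%. A one-sided paired t-test calibrated in the same way gives 73% at 28 pairs.

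**The case against.** The strongest objection is Table 5. The sentence right after the 30% figure plans 40 completers per site. Taken at face value, that leaves about 40 exercise pairs, and the Aim 3 requirement is met with room to spare. A reader who sees only 40 × 0.70 = 28 might infer that Aim 3 is underpowered outright. The documents do not support that unconditionally: it follows if 80 is the number randomised and fails if 80 is the number completing. The objection does not rescue the sufficiency statement either. Sections 1.3 and 3.1 give 80 as the number randomised, and no section gives the 115 or so that 80 completers would require.

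Three further points deserve a hearing.

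- **The meaning of 34.** The plan says participants, not pairs or participants per arm. The exercise-arm reading is an inference, though a strong one: the test is paired and one-sample, and the target is change with exercise.
- **Multiple imputation.** It keeps dropouts in the analysis and may reduce bias, but it does not restore the information in a follow-up sample that was never taken. The shortfall in observed pairs remains.
- **The 71% figure.** It is back-solved, not derived from the plan's inputs. The exercise study cited in 2.3.e reported 11.6%. Scaling the implied effect by 11.6/11 raises power at 28 pairs to about 76%. In the other direction, 2.3.e plans a Bonferroni correction that the sizing ignores. With an assumed 5 to 10 tests, the paired t-test at the implied effect has about 57% to 46% power at 34 pairs and 45% to 35% at 28. The 71% should not be read as the trial's actual Aim 3 power.

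A reader might also infer that Aim 2 fails, because its 28% tolerance is below 30%. The gap is one participant (29 against 28) and 80.7% against 79.2% power, which is negligible.

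**Conclusion.** The concern holds conditionally. If 80 is the number randomised, as sections 1.3 and 3.1 state and the Aim 2 allowance implies, the plan's own 30% attrition leaves about 28 exercise pairs against the 34 called sufficient. The statement is then true only if exercise-arm attrition is at most 15%, half the expected rate. If 80 is the number completing, as Table 5 plans, 34 pairs are available, but the stated number randomised is too small to produce them at 30% attrition. Either way one part of the plan has to change.

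The conclusion assumes that 34 means exercise-arm pairs, that allocation is 1:1, and that attrition is similar in both arms. The likely loss is moderate: about 9 percentage points of power on the calibration used here, with the true figure unknown because no SD is printed.

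**What to change.** 1. State whether 80 is the number randomised or the number completing, and make sections 1.3, 3.1 and 3.3.a (with Table 5) agree. If it is the number completing, give the number to be randomised and the attrition allowance behind it.
2. If 80 is the number randomised, replace the Aim 3 sufficiency sentence with three items: the expected 28 exercise-arm pairs; the 15% attrition at which 34 would still be reached; and the power, or the difference detectable with 80% power, at 28 pairs. The sponsor should recalculate the last item from its own source inputs, print the SD it uses, and say whether the figure is before or after the Bonferroni correction. The 71% and 12.2% given here are illustrations and should not be copied into the plan.

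If 80 is the number randomised, the cost is rewording only, with no added participants or procedures, and the stated Aim 3 power will probably look less favourable. If 80 completers are intended, the plan must acknowledge a larger randomised number, about 115 at 30% attrition, with the recruitment that implies.
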